### **Post-dose Spirometry**

The absolute change and relative (percent) change from the pre-dosing value to the post-dosing value of ppFEV1 on the same visit day will be provided by treatment group for the Day 1 and Day 15 visit. The descriptive statistics include the number of observations, mean, median, standard deviation, median, minimum and maximum.

In addition, the number and percentage of subjects with relative (percent) ppFEV1 decline  $\geq 10\%$  from the pre-dosing value at the Day 1 and Day 15 visit will be summarized by treatment group.

### **ECG**

ECG is collected at Screening, Day 15 and Day 29 visits. ECG findings will be summarized by treatment group for each visit. Summaries will include n (%) of patients in following categories:

- Normal

- Abnormal - Not Clinically Significant
- Abnormal - Clinically Significant
- Unable to Evaluate
- Missing

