5.5 Withdrawal of Subjects and Discontinuation of Study

A subject may voluntarily withdraw or be withdrawn from the study at any time for reasons including, but not limited to, the following:

- life-threatening AE or a serious adverse event (SAE) that places the subject at immediate risk; or maculopapular rash or other clinical manifestation of allergic drug reaction, for which the
-

severity is categorized as Common Terminology Criteria for Adverse Events (CTCAE, version 5.0) Grade 3 or higher

- worsening pulmonary status that, in the opinion of the investigator, is likely to respond to an approved and commercially available CFTR modulator therapy or that requires a significant change to the existing therapeutic regimen
- serious infections (e.g., requiring parenteral antimicrobial therapy and/or hospitalization)
- fungal infection requiring treatment with a triazole antimicrobial (e.g., fluconazole, itraconazole, voriconazole)
- confirmed pregnancy
- arrhythmia or conduction abnormality, including but not limited to prolonged QTcF, where the severity is categorized as CTCAE (version 5.0) Grade 3 or higher (QTc \geq 501 msec on at least 2 separate ECGs [at least 2 minutes apart] obtained within 10 minutes of the initial recording)
- If any of the following hepatic function test criteria is met, study drug must be discontinued immediately, the medical monitor must be notified, and a supplemental hepatic case report form must be completed (see Section 6.1):
 - AST and/or ALT elevations $> 8 \times$ ULN
 - AST and/or ALT elevations $> 5 \times$ ULN for more than 2 weeks
 - AST and/or ALT elevations $> 3 \times$ ULN, with total bilirubin $> 2 \times$ ULN
 - AST and/or ALT elevations $> 3 \times$ ULN, accompanied by clinical signs or symptoms suggestive for hepatic injury (fatigue, nausea, vomiting, right upper quadrant pain or tenderness, fever, rash, and/or eosinophilia [$> 5\%$]).

A thorough investigation of potential etiologies for the elevated transaminases should be conducted (e.g., trauma, acetaminophen use, viral hepatitis, alcohol ingestion), and the subject should be followed closely for clinical progression.

Subjects for whom treatment is discontinued for elevated hepatic function tests should have transaminases and bilirubin levels repeated by the central laboratory within 48 to 72 hours of the initial finding if possible, and then monitored closely until levels normalize or return to Baseline.

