3.6 Biomarker Sampling

Optional whole blood samples will be collected for biomarker research as specified in Section 2. All biomarker samples should be labeled and shipped as outlined in the study-specific laboratory manual. AbbVie (or people or companies working with AbbVie) will store the samples and data in a secure storage space with adequate measures to protect confidentiality. The samples may be retained while research on ABBV-3067 and ABBV-2222 (or drugs of this class) or cystic fibrosis (CF) and related conditions continues, but for no longer than 20 years after study completion, or per local requirements.

3.7 12-Lead Electrocardiogram

A 12-lead ECG will be performed at the designated study visits as specified in Section 2. The ECG should be performed prior to blood collection and after the subject has been resting supine for at least 5 minutes.

The ECGs will be evaluated by an appropriately trained physician at the site ("local reader"). The local reader from the site will sign and date all ECG tracings and will provide his/her global interpretation as a written comment on the tracing using the following categories:

- Normal ECG
- Abnormal ECG – not clinically significant
- Abnormal ECG – clinically significant

Only the local reader's evaluation of the ECG will be collected and documented in the subject's source folder. The automatic machine reading (i.e., machine-generated measurements and interpretation that are automatically printed on the ECG tracing) will not be collected. If an ECG at the Day 29 visit is interpreted as abnormal – clinically significant, it should be repeated at the follow-up visit or earlier, per the investigator's discretion until satisfactory clinical resolution or stabilization of the finding.

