### **9.3 Analysis of Laboratory Data**

Data collected from central and local laboratories, including additional laboratory testing due to an SAE, will be used in all analyses, except for Baseline where SAE-related laboratory assessments on or before the first dose of study drug will be excluded. The

clinical laboratory tests defined in the protocol operations manual (e.g., hematology and clinical chemistry) will be summarized.

Each laboratory variable will be summarized for all visits (starting with Baseline) with the number of non-missing observations, mean and standard deviation, median, minimum and maximum. Mean change from baseline to each applicable post-baseline visit will be summarized for laboratory variables with the number of observations, baseline mean, and visit mean. The change from baseline mean, standard error, and 95% confidence interval will be presented for the mean change from baseline within each treatment group.

In the DB Treatment Period, changes in selected laboratory parameters will be tabulated using shift tables for categories of low, normal, or high based on the normal ranges. A shift table from Baseline values of high or normal to post-Baseline low, or from Baseline values of low or normal to post-Baseline high will be created based on the worst post-Baseline value during treatment. Shifts from Baseline grade to the worst post-Baseline grade (CTCAE 4.03) during treatment will be summarized in a cross-tabulation of grades. Similar shift tables by normal range and grade will be provided for shifts from baseline to the final post-Baseline value.

Laboratory abnormalities for selected parameters will be evaluated based on Potentially Clinically Significant (PCS) criteria ([Appendix B](#)). For each laboratory PCS criterion, the number and percentage of subjects who have a laboratory value meeting the criteria during treatment will be summarized. A post-baseline value must be more extreme than the baseline value to be considered a PCS finding. Listings will be provided to summarize subject-level laboratory data for subjects meeting PCS criteria.

The number and percentage of subjects with laboratory values meeting the following criteria during treatment will be summarized to support the assessment of potential hepatotoxicity.

- ALT > 3 × ULN, > 5 × ULN, > 10 × ULN, > 20 × ULN
- AST > 3 × ULN, > 5 × ULN, > 10 × ULN, > 20 × ULN

- TBL > 1.5 × ULN, > 2 × ULN
- ALT and/or AST > 3 × ULN and TBL > 1.5 × ULN

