## **10.0 Other Analyses**

There are no other safety analyses planned for this study.

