## Appendix B. Potentially Clinically Significant Criteria for Safety Endpoints

The criteria for Potentially Clinically Significant (PCS) laboratory findings are described in Table B-1 and Table B-2, and the PCS criteria for vital sign findings are described in Table B-3.

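### The SAP tabulates ECG categories visit by visit without comparing subjects with their own baseline, so Normal to Abnormal – Not Clinically Significant changes, and the total worsening at either on-treatment visit, cannot be counted.

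*SAP*

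**What the plan says.** The 12-lead ECG is a listed safety endpoint (Protocol 3.3, SAP 3.4). Under the activity schedule (Protocol Appendix D) it is recorded at Screening, Day 15, and Day 29 or Premature Discontinuation, and not on Day 1. Operations Manual 3.7 keeps only the local reader's category; machine measurements are not collected.

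For the analysis, SAP 9.6 says: "ECG is collected at Screening, Day 15 and Day 29 visits. ECG findings will be summarized by treatment group for each visit". It continues: "Summaries will include n (%) of patients in following categories", and lists Normal, Abnormal – Not Clinically Significant (NCS), Abnormal – Clinically Significant (CS), Unable to Evaluate, and Missing.

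Nothing else is planned for ECG. SAP 10.0 says: "There are no other safety analyses planned for this study". SAP Appendix B gives potentially clinically significant (PCS) criteria for laboratory values, and "the PCS criteria for vital sign findings are described in Table B-3"; ECG has none. Protocol 7.4 likewise limits change-from-baseline and PCS summaries to laboratory tests and vital signs.

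Other safety data are compared within subject. For laboratory data, SAP 9.3 says: "Shifts from Baseline grade to the worst post-Baseline grade (CTCAE 4.03) during treatment will be summarized in a cross-tabulation of grades". For pulse oximetry, SAP 9.6 plans a shift from baseline category to the lowest on-treatment category. For vital signs, SAP 9.4 requires a PCS value to be more extreme than the subject's baseline.

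**The concern.** Separate totals at each visit do not show who changed. New abnormalities on treatment can be offset by earlier ones that resolve, leaving the totals level. Because the local reader's category is the only ECG result kept, no interval measurements can fill the gap.

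Safety data feed the choice of the ABBV-2222 dose for Part 2 (Protocol 3.1 and 4.1), and arms have only 9 or 18 subjects, so one or two newly abnormal subjects would be worth seeing when arms are compared. What is at stake is a complete description of ECG change, chiefly at its milder end. No primary conclusion depends on it.

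**Working it through.** The plan states no ECG figure, so there is nothing to reproduce. The question is whether the number of subjects who worsened can be recovered from totals at each visit.

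**Inputs.** Visits and categories come from SAP 9.6. The arm size of 18 comes from Protocol 4.1. The documents give no ECG abnormality rate, so every category count below is assumed. Missing data are ignored.

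**One post-baseline visit.** Let *n* be the arm size, *a*₀ the number abnormal at Screening and *a*₁ the number abnormal at the later visit. The number newly abnormal lies between max(0, *a*₁ − *a*₀) and min(*a*₁, *n* − *a*₀). With *n* = 18 and *a*₀ = *a*₁ = 5:

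- lower limit: max(0, 5 − 5) = 0, when the same five subjects are abnormal both times;
- upper limit: min(5, 18 − 5) = 5, when five different subjects are abnormal.

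Five is 5/18 = 28% of the arm, or 5/13 = 38% of those normal at Screening.

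**Either visit.** The smallest and largest numbers worsened, over all joint tables that agree with the totals for each visit, are:

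| Assumed Normal/NCS/CS at Screening; Day 15; Day 29 | Worse at Day 29 | Worse at Day 15 or Day 29 | New CS at either visit |
|---|---|---|---|
| 12/6/0; 12/6/0; 12/6/0 | 0 to 6 | 0 to 12 | 0 |
| 12/6/0; 11/6/1; 11/6/1 | 1 to 7 | 1 to 14 | 1 to 2 |
| 14/4/0; 13/5/0; 12/6/0 | 2 to 6 | 2 to 11 | 0 |

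These can be checked by hand.

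- Row 1: six subjects could be newly abnormal at Day 15 and a different six at Day 29, so 6 + 6 = 12, which is everyone normal at Screening.
- Row 2: at most seven can worsen at each visit (six Normal to NCS and one NCS to CS). With different subjects at the two visits, 7 + 7 = 14.
- Row 3: the upper limit is 5 + 6 = 11. The lower limit is 6 − 4 = 2, because only four of the six abnormal at Day 29 can have been abnormal at Screening.

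**Clinically significant findings.** Eligibility criterion 7 (Protocol 5.1) excludes these at Screening, so the Screening count should be about zero. The count at a later visit is then, in effect, the number newly CS at that visit. Row 2 shows what stays open: one case at each visit could be one subject or two.

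**Baseline.** SAP 8.1, in the efficacy section, defines baseline as the last non-missing value before first dose. With no Day 1 ECG scheduled, that is normally the Screening reading, so a baseline for a shift table exists.

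**The case against.** The strongest reply is that the part that matters most is already covered. Criterion 7 makes new CS findings readable at each visit. Protocol 6.1 requires an ECG judged a clinically significant worsening from baseline to be recorded as an adverse event, which then enters the treatment-emergent tables. Concurrent placebo arms allow abnormal percentages to be compared between arms at each visit. What is left is mainly change that the local reader judged not clinically significant.

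Most of this stands, and it sets the size of the point. It does not remove it. Adverse events are recorded as a diagnosis where possible and tabulated by system organ class and preferred term (Protocol 6.1, SAP 9.2.3), so they give no ECG total, and they run to 30 days after the last dose. Comparing arms by visit still does not show within-subject change.

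A reader might infer three stronger points that the documents do not support.

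- *Repeats after Day 29 are lost.* Operations Manual 3.7 says of a Day 29 ECG that "it should be repeated at the follow-up visit or earlier, per the investigator's discretion". That applies only when the Day 29 reading is already in the worst category, so a repeat cannot change the subject's worst result.
- *The recordings behind the QTc withdrawal criterion disappear.* Protocol 5.5 requires the value "on at least 2 separate ECGs [at least 2 minutes apart] obtained within 10 minutes of the initial recording". The criterion is CTCAE Grade 3 or higher and a listed reason for withdrawal, so the event should appear as an adverse event and, if study drug stops, in the discontinuation tables. The Premature Discontinuation visit also includes an ECG, in the same schedule column as Day 29.
- *Listing Missing as a category dilutes the abnormal percentage.* SAP 9.6 states no denominator for ECG, SAP 9.1 bases safety analyses on observed data, and the table shows every count, so a reader can recompute the percentage.

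**Conclusion.** The point holds in a limited form. No planned table gives the number of subjects who moved from Normal to NCS, or the number who worsened at either Day 15 or Day 29. It would go too far to say that ECG worsening in general cannot be read: worsening to CS is approximately readable at each visit, provided criterion 7 was applied, and should also be reported as adverse events.

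That the totals do not determine the number worsened does not depend on any particular counts; the width of the ranges does. The examples show that level totals can conceal change, not that a real signal would be missed. This is a minor improvement to the safety displays, and no decision in the documents is shown to depend on it.

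**What to change.** In SAP 9.6, add for each Part and arm a shift table from baseline ECG category (last pre-dose, normally Screening) to the worst category during treatment, with the order Normal, NCS, CS. Count the Day 15 ECG, the Day 29 or Premature Discontinuation ECG, and any recorded unscheduled on-treatment ECG. Base percentages on subjects with both a baseline and an on-treatment reading. Keep the by-visit table.

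Use the during-treatment window already applied to the laboratory and oximetry shifts rather than all recordings after first dose, and state that it includes the Day 29 visit, which falls the day after the last dose. Also say how a Premature Discontinuation ECG taken some days after the last dose is handled, since Protocol 5.6 asks for that visit preferably within 2 weeks.

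The cost is one more programmed table per Part. The scheduled readings are already collected, so no new ECGs or readers are needed. The documents do not confirm that unscheduled ECGs are entered in the database, so those can be counted only where recorded.

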## **10.0 Other Analyses**

There are no other safety analyses planned for this study.

## **11.0 Interim Analyses**

One interim analysis is planned when all of the subjects participating in study Part 1 have completed the Follow Up Period (including those who discontinue prior to the Follow Up visit) and the database has been locked for analysis. An additional interim analysis may be conducted when all of the subjects participating study Part 2 have completed or discontinued the Treatment Period and the database has been locked for analysis.

### **11.1 Data Monitoring Committee**

An external data monitoring committee (DMC) composed of persons independent of AbbVie and with relevant expertise in the Cystic Fibrosis field will review unblinded safety data from the ongoing study. The primary responsibility of the DMC will be to protect the safety of the subjects participating in this study.

A separate DMC charter describes the roles and responsibilities of the DMC members, frequency of data reviews, relevant data to be assessed, and general operations. In addition, the detailed data analysis and specifications for the DMC reviews are included in a separate DMC TFL specifications document.

## **12.0 Overall Type-I Error Control**

There is no multiple testing procedure planned for this dose ranging study.

Since Part 1 subjects and Part 2 subjects are two independent study populations and there is no plan to stop the study early for any efficacy claim after Part 1 is complete, no alpha spending is needed.

### 13.0 Version History

**Table 1. SAP Version History Summary**

Version	Date	Summary
1.0	10 Feb 2020	Original version
2.0	27 Jul 2021	
 
• Added plots for the primary endpoint and certain secondary endpoints in Section 8.1
 
• Clarified the missing data approach in Section 8.2
 
• Changed "rash related AESIs" to "rash AESIs" in Section 9.2.5
 
• For PCS labs in Section 9.3, changed "grade" to "value" in "post-baseline grade must be more extreme than baseline grade"
 
• Specifically mentioned CTCAE v. 4.03 for grade shift tables in Section 9.4
 
• Replaced specific categories of protocol deviations with a more general text in Appendix A
 

## **Appendix A. Protocol Deviations**

The number and percentage of subjects for each category in the collected protocol deviation data will be summarized.

## Appendix B. Potentially Clinically Significant Criteria for Safety Endpoints

The criteria for Potentially Clinically Significant (PCS) laboratory findings are described in Table B-1 and Table B-2, and the PCS criteria for vital sign findings are described in Table B-3.

**Table B-1. Criteria for Potentially Clinically Significant Chemistry Values**

Chemistry Variables	Units	Very Low	Very High
Total Bilirubin	mcmol/L		> 1.5 × ULN if baseline was normal; > 1.5 × baseline if baseline was abnormal
SGOT/AST	U/L		> 5.0 × ULN if baseline was normal; > 5.0 × baseline if baseline was abnormal
SGPT/ALT	U/L		> 5.0 × ULN if baseline was normal; > 5.0 × baseline if baseline was abnormal
Albumin	g/L	< 20	
Glucose	mmol/L	< 2.2	> 13.9
Creatinine	mcmol/L		> 1.5 × ULN or 1.5 × baseline
Sodium	mmol/L	< 130	> 155
Potassium	mmol/L	< 3.0	> 6.0
Calcium	mmol/L	< 1.75	> 3.1
CPK	U/L		> 5.0 × ULN
Total Cholesterol	mmol/L		> 10.34
GGT	U/L		> 5.0 × ULN if baseline was normal; > 5.0 × baseline if baseline was abnormal
Alkaline phosphatase	U/L		> 5.0 × ULN if baseline was normal; > 5.0 × baseline if baseline was abnormal

Note: A post-baseline value must be more extreme than the baseline value to be considered a potentially clinically significant finding.

**Table B-2. Criteria for Potentially Clinically Significant Hematology and Coagulation Values**

Hematology Variables	Units	Very Low	Very High
Hemoglobin	g/dL	< 8.0	
Platelets count	10  /L	< 75.0	
WBC count	10  /L	< 2.0	
Neutrophils	10  /L	< 1.0	
Lymphocytes decrease	10  /L	< 0.5	
Reticulocyte count	10  /L		> ULN and > baseline
INR	N/A		>1.5

Note: A post-baseline value must be more extreme than the baseline value to be considered a potentially clinically significant finding.

**Table B-3. Criteria for Potentially Clinically Important Vital Sign Values**

Vital Sign	Category	Criteria for Potential Clinically Significant Vital Signs	Reference
Systolic blood pressure	Low	Value $\leq$ 90 mmHg and decrease $\geq$ 20 mmHg from Baseline	Vaccine Trial Guidance, Grade 1 or above
	High	Value $\geq$ 160 mmHg and increase $\geq$ 20 mmHg from Baseline	CTCAE, Grade 3 or above, 2018 ESC/ESH guidelines
Diastolic blood pressure	Low	Value $\leq$ 50 mmHg and decrease $\geq$ 10 mmHg from Baseline	
	High	Value $\geq$ 100 mmHg and increase $\geq$ 10 mmHg from Baseline	CTCAE, Grade 3 or above, 2018 ESC/ESH guidelines
Pulse	Low	Value < 50 bpm and decrease $\geq$ 15 bpm from Baseline	Vaccine Trial Guidance, Grade 2 or above
	High	Value $\geq$ 116 bpm and increase $\geq$ 15 bpm from Baseline	Vaccine Trial Guidance, Grade 2 or above
Weight	Low	$\geq$ 5% decrease from baseline	CTCAE, Grade 1 or above
	High	$\geq$ 10% increase from baseline	CTCAE, Grade 2 or above
Temperature	High	> 39.0	CTCAE, Grade 2 or above
Oxygen saturation	Low	< 90%	

ESC = European Society of Cardiology; ESH = European Society of Hypertension

Note: A post-baseline value must be more extreme than the baseline value to be considered a potentially clinically significant finding.
